5.4 Quantifying health resource use (HRU) and costs

The following HRU outcomes and associated costs will be tabulated for each of the comorbidity clusters identified in phase 1. These will be for the year prior to the index date. Secondary care resource use and costs will be limited to patients with linked secondary care (HES) data and the most recent HES year. Costs will be reported in 2017 GB pounds.

Primary care

1. Physician office visits:
 - a. Number and cost of asthma-related consultations.
2. Number of primary care medication prescriptions:
 - a. ICS
 - b. ICS/LABA
 - c. SABA
 - d. SAMA
 - e. LABA
 - f. LAMA
 - g. LABA/LAMA
 - h. LTRA
 - i. biologics (where known)
 - j. chronic oral corticosteroids
 - k. antibiotics
3. Total cost of asthma drug prescribing.
4. Total cost of oral corticosteroid and antibiotic prescribing.
5. Total primary care costs (physician office visits + prescribing).

Secondary care

6. Outpatient visits:
 - a. Number and cost of asthma-related outpatient visits.
7. Emergency Room attendances:
 - a. Number and cost of asthma-related Emergency Room attendances.
8. Inpatient hospital admissions:
 - a. Number and cost of asthma-related hospital admissions.
9. Total secondary care costs (outpatient + ER + inpatient).

Combined primary and secondary HRU and costs

11. Total primary and secondary care costs (primary care + secondary care).

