3.2 Study design

A two-phase historical cross-sectional and cohort study using routine electronic patient records from UK primary care practices. The study period will be 2010-2017 (or the latest available data). It will include patients with active asthma. In Phase 1 the frequency of each combination of comorbidities will be estimated using most recent clinical data available for each eligible patient. In Phase 2, the clinical characteristics and service use in a 1-year period after the date of co-morbidity assessment will be described for a pre-selected set of common comorbidity clusters.

[figure not shown]

Figure 1: Study design Phase 2

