4.2 Inclusion and exclusion criteria

Inclusion criteria

Registered at a participating practice for at least one year prior to their index date and within the study period. In phase 1, the cross-sectional assessment of co-morbidity co-occurrence, the index date for each patient will be the earlier of the following dates: the last data collection from each practice and 6 months before patient deregistration (to avoid gaps in the clinical data due to late recording of patient deregistrations). For CPRD practices with linked HES data, the index date will be the earliest of the following dates: the last data collection from each practice, 6 months before patient deregistration, date of last HES record. In phase 2, the index date will be one year before the last data collection from each practice and 6 months before patient deregistration, to allow for one year of follow-up.

Patient had active asthma at their index date:

- a diagnosis of asthma at any time before their index date (using QOF Read codes: see Appendix 1); AND
- two or more prescriptions for an asthma medication in the preceding year.

Exclusion criteria

Any other chronic lower respiratory condition recorded at any time (Read coded: see Appendix 2). These are:

- Lung disease due to external agents, other than smoking, such as occupational agents.
- Active COPD (a Read code at any time + medication in the last year of follow-up).
- Bronchiolitis obliterans.
- Pulmonary fibrosis.
- Pulmonary hypertension.
- Cystic fibrosis

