5.3 Categorising comorbidity activity and severity

Many of the comorbidities can be further characterised as inactive or active, and mild or moderate/severe at the index date using prescribing and primary and secondary consultation data. A comorbidity will be defined as inactive in the year prior to the index date if it was not classified as active. Similarly, a comorbidity will be defined as mild in the year prior to the index date if it was not classified as moderate/severe.

Following a rapid review of the definitions applied by studies using routine patient data and prescribing guidelines, the following definitions were adopted.

Note on medications with more than one indication

The indication for a prescription may not be recorded as the time it is issued and some medications can be indicated for more than one of the comorbidities of interest. Following a review of the approaches used in other published studies, the diagnosis recorded closest in time to the initiation of the medication will be taken as the indication. Similarly, the reason for outpatient consultations is not routinely coded in HES data and individual hospital specialties may treat more than one of the comorbidities of interest (e.g. ENT treating both allergic rhinitis and chronic rhinosinusitis). Where this occurs we will attribute the outpatient consultation to the diagnosis recorded closest in time to the secondary care consultation.

Atopic dermatitis

Active: A primary or secondary care consultation in the previous year. Prescription of a topical corticosteroid in the previous year.

Moderate/severe: A primary or secondary care consultation in the previous year. Prescription of a medium- to high-potency topical corticosteroid in the previous year (see Appendix 6 for categorisation of topical corticosteroid preparations).

Allergic Rhinitis

Active: A primary or secondary care consultation in the previous year. Prescription of a nasal corticosteroid in the previous year.

Moderate/severe: A primary or secondary care consultation in the previous year. Three or more nasal corticosteroid in the previous year.

Chronic Rhinosinutis

Active: Always active as this is a chronic condition.

Moderate/severe: A primary or secondary care consultation in the previous year. Three or more nasal corticosteroid prescriptions in the previous year.

Nasal polyps

Active: Always active.

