6.7 Healthcare resource utilisation (HRU) and costs (phase 2)

The HRU outcomes and associated costs will be calculated and reported for each of the outcomes of interest in the year prior to the index date (mock table in appendix 12).

Associations between specific co-morbidity patterns and healthcare resource utilisation and costs will be estimated using generalised estimating equations with cluster robust standard errors, log link and gamma distribution, adjusting for confounders.

Secondary care resource use and costs will be limited to patients whose practices have linked secondary care (HES) data.

Prices assigned to primary care consultation costs will be taken from the latest Personal Social Services Research Unit (PSSRU) document (<http://www.pssru.ac.uk/project-pages/unit-costs/2017/index.php>)

Prices assigned to secondary care costs will be based on the national average hospital costs as found in PSSRU document.

Prices assigned to drugs will be taken from the Dictionary of Medicines and Devices browser (<http://dmd.medicines.org.uk/>). The electronic British National Formulary (eBNF) and the Medical Index of Medicinal Substances (MIMS) will be used to fill any gaps.

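### Phase 2 resource use and costs are placed after the index date in sections 3.2 and 4.2 but before it in sections 5.4 and 6.7, and secondary care has an anchor of its own

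*Protocol*

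**What the plan says.** Protocol section 3.2 states that in Phase 2 "the clinical characteristics and service use in a 1-year period after the date of co-morbidity assessment will be described". Section 4.2 supports this: "In phase 2, the index date will be one year before the last data collection from each practice", with a condition on deregistration, and the reason given is "to allow for one year of follow-up". Section 5.3 fixes the assessment date, because comorbidities are classed as "inactive or active, and mild or moderate/severe at the index date using prescribing and primary and secondary consultation data". The assessment date is therefore the index date.

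Section 5.4 then says of the resource-use and cost outcomes: "These will be for the year prior to the index date". Section 6.7 says they are reported "for each of the outcomes of interest in the year prior to the index date". Section 5.4 adds a further condition: "Secondary care resource use and costs will be limited to patients with linked secondary care (HES) data and the most recent HES year". Its last item sums primary and secondary care costs. The mock table in Appendix 12 refers to a year without saying which.

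**The concern.** Two programmers working from different sections would analyse different years. Under 3.2 and 4.2 the resource-use analysis is a cohort analysis, with comorbidity established first and service use counted afterwards. Under 5.4 and 6.7 it is cross-sectional. Resource use and costs are part of the Phase 2 primary objective (section 2.2), alongside demography and asthma severity, and section 6.7 fits adjusted models to them, so the choice of year changes what is estimated.

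The pre-index window has a specific weakness. For many conditions, section 5.3 decides activity and severity from consultations and prescriptions in that same year. A year of frequent contact can move a patient into the active or moderate/severe group and also raise that year's asthma-related use. Section 6.6 plans to examine clusters by comorbidity severity and activity, so the overlap affects planned comparisons.

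**Working it through.** The check is a comparison of time windows; the plan gives no figure to reproduce.

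**Notation.** L is last data collection, D is deregistration and H is the end of HES coverage. All offsets are in months.

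**1. Patient still registered at L.** Section 4.2 gives index = L − 12.
- Window in 3.2: index to index + 12 = (L − 12, L).
- Window in 5.4 and 6.7: index − 12 to index = (L − 24, L − 12).
- Overlap: 0 months of 12.

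The windows would coincide only if comorbidity were assessed a year before the index. Sections 4.2 and 5.3 rule that out. No resource-use or cost outcome in 5.4 or 6.7 is explicitly placed in (L − 12, L).

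**2. Overlap with the exposure window (section 5.3).**
- Activity is decided by contacts or prescriptions in four of the nine conditions: atopic dermatitis, allergic rhinitis, urticaria (consultations over two years) and allergic conjunctivitis. The other five are always active.
- Severity uses at least one criterion from the previous year in eight of the nine. Eosinophilic oesophagitis is always moderate/severe.
- Presence (section 5.2) needs only a Read code in the record, or an adrenaline prescription for anaphylaxis, with no one-year limit.

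The shared year therefore bears mainly on contrasts by activity or severity, and less on plain cluster membership.

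**3. Secondary care window.** Section 4.2 can be read in two ways for HES-linked patients.
- Reading A applies the rule for linked CPRD practices: index = earliest of L, D − 6 and the last HES record. If the HES date H is earliest, the pre-index year is (H − 12, H), which is also the latest HES year. Section 5.4 is then consistent with itself, but no HES follow-up exists after the index.
- Reading B applies the Phase 2 rule: index = L − 12. Primary care use falls in (L − 24, L − 12) and the latest HES year is (H − 12, H). With H = L − d, the overlap is d months for d from 0 to 12. It is 0 if HES runs to L, and complete only at d = 12.

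Whether the combined total mixes periods thus depends on the index rule and on HES coverage, which the protocol does not give.

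**4. Deregistered patients.** The Phase 2 sentence can mean 12 months before the earlier of L and D − 6, or the earlier of L − 12 and D − 6. On the second reading, a patient indexed at D − 6 has 6 months of registration left, not 12.

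**5. Can the inflation be sized?** Not from the documents. An illustration on assumed inputs: 2,000,000 patients; 0.3 comorbidity and 2 asthma contacts a year; stable gamma frailty with variance 0.3; year-specific gamma frailty with variance 0.25 to 0.5; no causal link. The ratio is mean asthma contacts, exposed over unexposed.

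| Assumption | Same year | Next year |
|---|---|---|
| Active vs inactive, year effect shared by both contact types | 1.74–2.14 | 1.32–1.35 |
| Active vs inactive, independent year effects | about 1.33–1.34 | about 1.33–1.34 |
| Ever coded vs not, 10-year record, coding rate 0.03–0.10 a year, shared year effect | 1.40–1.61 | 1.36–1.51 |

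The gap between windows runs from nil to large according to the assumption, and the next-year ratio stays above 1 throughout.

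**The case against.** The best defence is that a year-prior window is legitimate in a descriptive study, that section 3.2 calls the design both cross-sectional and cohort, and that the HES clause in 4.2 can make the year before the index the same as the latest HES year. This last point stands as one reading, so the protocol cannot be said always to add two different years. It does not reconcile 3.2 and 4.2 with 5.4 and 6.7, which state opposite directions in plain words.

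Several stronger inferences should be resisted.
- A reader might infer that the models adjust for their own outcome, because Risk Domain Asthma Control counts the same hospital events. Section 5.1 lists it only as a characteristic, and section 6.8 names no covariates.
- A reader might take the largest simulated ratios as the expected bias. They rest on assumed rates and on a shared year effect, and they compare active with inactive disease, whereas 5.4 and 6.7 work by cluster or comorbidity pattern. The visit outcomes are also asthma-related only.
- A reader might say that the design in 3.2 avoids the problem. It does not, because stable differences between patients carry over into the next year.
- A reader might say that the follow-up year is wholly unused. The COPD exclusion refers to a last year of follow-up, and the latest HES year could fall after the index.

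Figure 1 is not shown and cannot be checked, but it could not alter the wording of 5.4 and 6.7. The statistical analysis plan may add detail, but the protocol would still contain both windows.

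**Conclusion.** The contradiction is established on the text. The design and index sections put Phase 2 service use after the index; the outcome and analysis sections put it before. The windows share 0 of 12 months for a patient still registered at last data collection. Because 5.4 and 6.7 agree with each other, this is not a single slip.

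Two consequences follow with qualification. First, the pre-index window shares its year with the contacts that define activity for four conditions and severity for eight, which can inflate associations by activity or severity by an amount the documents do not determine. Second, the secondary care period need not match the primary care period in the combined cost; this depends on which index rule in 4.2 applies and on where HES coverage ends. Confidence is high for the contradiction and lower for its numerical effect. It should be resolved before the Phase 2 data are specified.

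**What to change.** - In 5.4, 6.7 and Appendix 12, define all primary and secondary care resource use and costs over the same 12 months after the Phase 2 index date. Pre-index use may stay as a baseline description only.
- In 5.4, replace the restriction to the latest HES year with that same window, for HES-linked patients.
- In 4.2, set the Phase 2 index 12 months before the earliest of last data collection, 6 months before deregistration and, for HES-linked patients, the end of HES coverage. In the notation above, index = min(L, D − 6, H) − 12, so the window ends at min(L, D − 6, H) and is fully covered. State that this replaces the HES index clause for Phase 2.

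The cost is slightly more than wording, because the index rule itself changes. Some patients will be indexed earlier, and a few may no longer have the required year of prior registration. Cross-associations from stable patient differences will remain and should be acknowledged in the interpretation.

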6.8 Confounding handling approach

The multivariable models will be adjusted on variables that are known or show to confound the association of interest. For this we will use both expert opinion and a data driven technique using bias potential.

Expert opinion will decide what set of baseline characteristics will always be adjusted on in the models. Also, expert opinion will decide on the set of candidate confounders to consider in the next step, using bias potential assessment. This assesses the degree to which the observed association between the exposure of interest and the outcome is affected by conditioning on the variable. It measures the relative change in coefficient of the exposure compared to the model without the candidate confounder. Confounder candidates will be introduced into the model iteratively, the one with the highest bias potential first. If the observed change in estimate is more than 2%, the variable is kept in the model, and all remaining candidates are re-evaluated until none of the confounder candidates are left or none cause a change in estimate of more than 2%.

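### Sections 3.2 and 4.2 set Phase 2 service use in the year after the index date; sections 5.4 and 6.7 set resource use and cost in the year before it, and 5.4 adds an unanchored HES year.

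*Protocol*

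**What the plan says.** Two sections of the protocol look forward from the index date and two look back.

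- **Section 3.2 (study design):** in Phase 2, "the clinical characteristics and service use in a 1-year period after the date of co-morbidity assessment will be described" for the selected clusters.
- **Section 4.2 (eligibility):** "In phase 2, the index date will be one year before the last data collection from each practice and 6 months before patient deregistration", and the stated reason is "to allow for one year of follow-up".
- **Section 5.4 (resource use and costs):** "These will be for the year prior to the index date". Secondary care is further limited to "the most recent HES year".
- **Section 6.7 (resource use and costs, phase 2):** outcomes are "calculated and reported for each of the outcomes of interest in the year prior to the index date".

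Other items are also placed in the year before the index date. Active asthma needs "two or more prescriptions for an asthma medication in the preceding year" (4.2). Section 5.1 takes GINA step, Risk Domain Asthma Control (RDAC) and asthma medication from that year. Section 5.3 grades comorbidity activity and severity mostly from that year. On adjustment, section 6.8 states: "Expert opinion will decide what set of baseline characteristics will always be adjusted on in the models".

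**The concern.** Resource use and costs are part of the Phase 2 primary objective in section 2.2. An analyst working from 3.2 and 4.2 would measure them after the index date. An analyst working from 5.4 and 6.7, the sections that define and analyse these outcomes, would measure them before it. The two would report results from different years of the same patients' records.

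If 5.4 and 6.7 are followed, the year that 4.2 set aside is not used for these outcomes, and the outcome year is also the year that admits patients to the study. Three consequences follow:

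1. Total asthma prescribing cannot fall below the two prescriptions needed for entry.
2. Any breakdown by comorbidity activity or severity uses gradings drawn largely from the outcome year.
3. If a baseline variable such as GINA step or RDAC is chosen as a confounder, the outcome is adjusted for some of its own components.

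**Working it through.** There is no stated figure to reproduce: section 6.1 gives only available patient counts. The check is date arithmetic in months, with last data collection at L and a patient who has not deregistered.

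**Inputs.** The Phase 2 index date is L - 12 (4.2). Follow-up lasts 12 months (3.2, 4.2). The outcome window is the 12 months before the index date (5.4, 6.7). Eligibility, GINA step, RDAC and asthma medication use the 12 months before the index date (4.2, 5.1).

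**Overlap** of two windows = max(0, earlier end - later start).

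| Window for resource use and cost | Months | Overlap with follow-up year (L-12 to L) | Overlap with eligibility/baseline year (L-24 to L-12) |
|---|---|---|---|
| As in 3.2 and 4.2 | L-12 to L | 12 | 0 |
| As in 5.4 and 6.7 | L-24 to L-12 | 0 | 12 |

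**The HES year.** Section 5.4 does not tie it to the index date, and the protocol does not say when HES coverage ends relative to L. If the last HES year ends h months before L (assumed values), the window is L-h-12 to L-h:

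| h | Overlap with follow-up year | Overlap with pre-index year |
|---|---|---|
| 0 | 12 | 0 |
| 6 | 6 | 6 |
| 12 | 0 | 12 |
| 18 | 0 | 6 |
| 24 | 0 | 0 |

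Primary and secondary care costs, which 5.4 adds together, could therefore come from different years.

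**Deregistered patients.** The Phase 2 rule in 4.2 joins two dates with a bare conjunction and does not say which governs. Take deregistration at D and read the rule as the earlier of L - 12 and D - 6:

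- D = L-3: the index date is the earlier of L-12 and L-9, so L-12. Registered follow-up is 12 - 3 = 9 months.
- D = L-6: the index date is L-12. Registered follow-up is 12 - 6 = 6 months.
- D = L-12: the index date is L-18. Registered follow-up is 18 - 12 = 6 months.

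On this reading some patients lack the year of follow-up that 4.2 intends. If instead 12 months are subtracted from the earlier of L and D - 6, each of these patients has 18 registered months after the index date, 12 of them before the six-month cut-off.

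**What falls inside the pre-index year.**

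- *Entry rule.* It counts any asthma medication. Total asthma prescribing is therefore at least two in that year, but a single drug class can still be 0 or 1. Antibiotics, consultations and secondary care have no such floor.
- *RDAC.* It is built from asthma-related A&E, inpatient and outpatient events, the event types of outcomes 6 to 8 in 5.4, and from acute oral steroid and antibiotic courses, which overlap with outcome 4. GINA step is set by that year's prescribing.
- *Activity.* Five of the nine comorbidities are always active. The other four depend on recent data, and urticaria's consultation criterion reaches back two years.
- *Severity.* Most criteria use one year; some use two years, 30 months or any time.
- *Cluster membership.* It is a Read code in the record with no one-year limit (5.2), so it is not tied to the outcome year.

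**The case against.** The strongest reconciling reading is that 5.4 means the Phase 1 index date, which for these patients is L. The year before it is L-12 to L, exactly the Phase 2 follow-up year. But neither 5.4 nor 6.7 says so, 6.7 is headed phase 2, and 4.2 defines a separate Phase 2 index date. Figure 1 is not available here; it could show which window was intended, but it would not make the four statements agree. Nor can the choice simply be left to an SAP, because the protocol states two windows rather than leaving one open.

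It is also fair to say that the objective in 2.2 is descriptive and that a same-year cost profile could serve it. That is true, but it is not the design in 3.2, and it would leave the index shift in 4.2 without a purpose for these outcomes.

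Three stronger readings are tempting and are not supported:

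- *That the follow-up year is never used.* Section 3.2 states the intention to use it, the HES year and the COPD exclusion's medication criterion may fall in it, and the severity regression in 6.6 gives no outcome window.
- *That the exposure shares the outcome window.* Section 6.7 models comorbidity patterns, and membership is any Read code. Only the activity and severity gradings, used in 6.6, largely share it.
- *That the models adjust the outcome for itself.* Section 6.8 leaves the confounder list to expert opinion, so this holds only if such a variable is chosen.

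**Conclusion.** The contradiction is plain on the text and must be resolved before programming. The two windows share 0 months, and the one in 5.4 and 6.7 coincides in full, 12 of 12 months, with the year that sets eligibility, GINA step, RDAC and asthma medication. This rests on a patient who has not deregistered and on the index date in 5.4 and 6.7 being the Phase 2 date.

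Followed as written, 5.4 and 6.7 turn the resource-use and cost analysis into a same-year cross-section, with total asthma prescribing bounded below by the entry rule. Adjustment of the outcome for its own components is a conditional risk.

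How far cluster cost ratios would move cannot be derived from the document. It gives no prescribing rates, variances or year-to-year correlation, so any figure would reflect assumed inputs. Moving the window also would not remove every effect of adjusting for treatment-based covariates.

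**What to change.** 1. **Sections 5.4 and 6.7:** measure resource use and cost in the year after the Phase 2 index date. Keep eligibility, comorbidity grading and covariates before it. Prior-year resource use may be reported as baseline description.
2. **Section 5.4:** replace the most recent HES year with the same post-index year, so that primary and secondary care costs cover the same 12 months.
3. **Section 4.2:** define the Phase 2 index date as the earliest of 12 months before last data collection, 12 months before the deregistration cut-off (itself six months before deregistration) and, for HES-linked patients, 12 months before the end of HES coverage. The Phase 2 sentence currently sets no HES limit.

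The cost is wording in three sections. No new primary care data are needed, since the index date is already set back a year. Some HES-linked or deregistered patients may get a somewhat earlier index date, and slightly fewer of them may remain eligible.

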5.0 Study variables and study outcome definitions

5.1 Describing demographic and clinical variables

The demographic and clinical characteristics of interest at index date are: gender, age, smoking status, most recent recorded BMI prior to index date, most recent spirometry recorded prior to index date (PEF, FEV₁, FEV₁/FVC ratio), number with severe asthma, GINA step, Risk Domain Asthma Control and Overall Asthma Control, asthma medications in the year prior to index date, blood eosinophil count.

- Smoking status will be categorised as: never smoked; ex-smoker; or current smoker based on the latest recorded Read code prior to the index date.
- Body Mass Index (BMI) will be calculated from height and weight data if available (weight in kg/height in m²) or taken from the practice recorded BMI value if not.
- The most recently recorded Peak Expiratory Flow (PEF), Forced Expiratory Flow in one second (FEV₁) and Forced Vital Capacity (FVC) will be taken from the practice recorded value. FEV₁/FVC ratio will be calculated using the last recorded of each of these two values. FEV₁% predicted will also be calculated and reported,
- Severe asthma will be defined according to the ERS/ATS guidelines (Chung, Kian Fan, et al. "International ERS/ATS guidelines on definition, evaluation and treatment of severe asthma." European Respiratory Journal (2013): erj02020-2013).
- We will also report the number of patients meeting the definition of severe asthma used in Regeneron RCTs.
- GINA step will be determined by prescribed medication: see Appendix 4. Highest GINA step (1-5) in the year prior to the index date will be reported.
- Risk Domain Asthma Control (RDAC). Controlled asthma will be defined as the absence of the following in the year prior to the index date: (i) an asthma-related A&E attendance, in-patient admission or out-patient department attendance; (ii) an acute course of oral corticosteroids with evidence of a lower respiratory consultation; and (iii) an antibiotic prescribed with evidence of a lower respiratory consultation.

- Overall Asthma Control. Controlled asthma will be defined as the absence of the following aspects of asthma risk during the baseline year: attainment of RDAC and an average daily dose of ≤ 200 mcg salbutamol / ≤ 500 mcg terbutaline.

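### Section 5.4 limits contacts and asthma drug cost to asthma but sets no indication limit on antibiotics or on oral corticosteroid and antibiotic cost, so the totals have a mixed scope and cluster comparisons may be biased upward

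*Protocol*

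**What the plan says.** Section 5.4 sets the scope of the resource-use outcomes line by line. Each type of contact is limited to asthma: "Number and cost of asthma-related consultations" in primary care, then "Number and cost of asthma-related outpatient visits", "Number and cost of asthma-related Emergency Room attendances" and "Number and cost of asthma-related hospital admissions". Item 3 is likewise confined to asthma drugs.

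Item 2k lists antibiotics with no qualifier. Item 4 is "Total cost of oral corticosteroid and antibiotic prescribing", again with no indication stated and no split between acute and chronic OCS. Item 2j counts chronic OCS only.

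The sums follow. Item 5 is "Total primary care costs (physician office visits + prescribing" (closing bracket omitted), item 9 adds the three secondary care lines, and item 11 is "Total primary and secondary care costs (primary care + secondary care" (likewise).

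Section 5.1 treats the same drugs differently. Under Risk Domain Asthma Control, an acute OCS course counts only when there is evidence of a lower respiratory consultation, and so does "an antibiotic prescribed with evidence of a lower respiratory consultation".

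**The concern.** Resource use and cost belong to the Phase 2 primary objective (section 2.2). Section 6.7 models them against comorbidity pattern with generalised estimating equations, using a log link and gamma distribution. The exposure is therefore the set of comorbidities, some of which may themselves be treated with OCS or antibiotics. If those prescriptions enter an outcome that otherwise counts only asthma care, a cluster can look more expensive with no difference in asthma care.

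The confounder selection in section 6.8 cannot remove this. The extra prescribing comes from the exposure and sits inside the outcome definition; it is not a third variable to condition on. A total built this way also cannot be read as all-cause cost, because visits and other drugs for the comorbidities are left out.

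**Working it through.** The protocol states no cost, prescribing rate or effect size, so there is no figure to reproduce. The check is one of text, followed by an illustration of size.

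**Step 1: scope of each line in section 5.4**

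| Line | Scope as written |
|---|---|
| Item 1a, consultations | asthma |
| Item 3, asthma drug cost | asthma |
| Item 2k, antibiotics (count) | no limit stated |
| Item 4, OCS and antibiotic cost | no limit stated; acute and chronic not separated |
| Items 6a, 7a, 8a, secondary care contacts | asthma |
| Item 5 | visits plus prescribing; does not say whether prescribing is item 3 or items 3 and 4 |
| Item 11 | primary plus secondary care totals |

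The natural reading of item 5 takes in both prescribing costs. Item 4 then passes into items 5 and 11. Item 2k is a count and enters no cost total itself.

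**Step 2: does another section supply the rule?**

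- Section 5.1 has a lower respiratory rule, but only for asthma control and, for OCS, only for acute courses.
- Section 5.3 attributes a drug with several indications to the diagnosis nearest in time. It is written to classify the nine comorbidities. Asthma is not one of them, and section 5.4 does not take the rule up.
- Appendix 12 heads its prescribing block as asthma, with rows elided, and closes it with the asthma prescribing total (item 3). More rows are elided before the primary care total, which is where item 4 would fall in list order. The table neither confirms nor excludes use for other indications.

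**Step 3: direction**

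The literature review in Appendix 13 names OCS among the treatments that mark steroid-refractory eczema. That supports higher OCS use in severe eczema irrespective of asthma. For antibiotics, and for sinus and polyp disease, a similar direction is plausible but not documented.

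**Step 4: illustrative size on cost (all inputs assumed)**

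Set the true asthma cost to 100 in both cluster and reference, so the true ratio is 1.00. Let s be the non-asthma OCS and antibiotic cost in the reference group, as a percentage of asthma cost, and k its multiple in the cluster.

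Ratio = (100 + s × k) / (100 + s)

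- k = 1, any s: 1.00
- s = 1, k = 1.5: 101.5 / 101 = 1.005
- s = 5, k = 2: 110 / 105 = 1.05
- s = 10, k = 3: 130 / 110 = 1.18

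**Step 5: illustrative size on the antibiotic count in item 2k (all inputs assumed)**

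Let b be yearly lower respiratory courses (equal in both groups), o the other courses in the reference and x the extra courses in the cluster.

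Ratio = (b + o + x) / (b + o)

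- b = 0.6, o = 0.2, x = 0.2: 1.0 / 0.8 = 1.25
- b = 0.6, o = 0.4, x = 0.8: 1.8 / 1.0 = 1.80

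These are ratios of counts and say little about cost. They show only that the count line is more exposed than the totals.

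**The case against.** The protocol never says these drugs are counted whatever the indication; that is inferred from a missing qualifier. The asthma heading in Appendix 12 leaves a narrower reading open, and section 5.1 lists chronic OCS among the asthma medications. Section 6.6 leaves the final list of Phase 2 tables until that phase begins, and attribution of prescriptions is often settled in an analysis plan. Items 3 and 4 are separate lines, so a reader can already see asthma drug cost without the disputed part. The totals also state their components.

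Much of this stands. A reader might infer that the protocol deliberately counts OCS and antibiotics for every indication, and that total cost is therefore inflated in sinus, polyp and skin clusters. The documents support neither as fact. They give no prescribing rates or costs, item 5 does not say outright that it includes item 4, and at equal use across clusters the ratio is unbiased.

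A further objection is sound: section 5.1 ties only acute OCS courses to a lower respiratory consultation. Extending that rule to all OCS could drop maintenance OCS given for asthma, which Appendix 4 places at GINA step 5, and so understate cost in the most severe patients.

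The objection does not dispose of the point. The protocol itself fixes this outcome list, limits the neighbouring lines to asthma and leaves these two open, against its own rule in section 5.1. That is an inconsistency in the document, not a detail left for later.

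**Conclusion.** The point holds as a mixed and ambiguous outcome definition. Read literally, items 5 and 11 combine asthma-only contacts and asthma drugs with OCS and antibiotics of unstated indication, so they measure neither asthma cost nor all-cause cost. Cluster comparisons of OCS and antibiotic use may be biased upward where those drugs treat the comorbidity; comparisons of cost less so.

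The range of 0 to about 18% on a total-cost ratio rests wholly on assumed values of s (1 to 10%) and k (1 to 3). It is not an estimate for this study. Direction has documentary support only for OCS in refractory eczema. The point should be settled before Phase 2, since it touches a primary-objective outcome and adjustment cannot repair it.

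**What to change.** 1. In items 2k and 4, count antibiotics and acute OCS courses towards the asthma totals only with evidence of a lower respiratory consultation, as in section 5.1. Show all-indication use in a separate row outside the totals.
2. Split item 4 into acute and chronic OCS with the Appendix 5 algorithm. Do not apply the lower respiratory rule to chronic OCS. State a separate attribution rule for it, for example the nearest-diagnosis rule of section 5.3 extended to include asthma. Since section 5.1 counts chronic OCS as an asthma medication, also say whether it is costed in item 3 or item 4, so that it is not summed twice.
3. State that item 5 is the sum of items 1, 3 and the restricted item 4, and label items 5, 9 and 11 as asthma-related.

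The cost is small: an algorithm already in the protocol, one attribution rule to write, and table labels. No new data are needed. The downside is that true asthma courses without a coded consultation will be missed; the all-indication row makes the possible extent visible.
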